8.2 Data collection

Designated investigator staff will enter the data required by the protocol into the OC/RDC system. Designated investigator site staff will not be given access to the system until they have been trained.

Automatic validation procedures within the system check for data discrepancies during and after data entry and, by generating appropriate error messages, allow the data to be confirmed or corrected online by the designated investigator site staff. The Investigator must certify that the data entered into the eCRFs are complete and accurate. After database lock, the investigator will receive copies of the patient data for archiving at the investigational site.

8.3 Database management and quality control

Novartis staff [or CRO working on behalf of Novartis] review the data entered into the eCRFs by investigational staff for completeness and accuracy and instruct the site personnel to make any required corrections or additions. Queries are sent to the investigational site using an

Novartis	Confidential	Page 70
Amended Clinical Trial Protocol Version 0	3 clean	Protocol No. CAIN457F3301

electronic data query. Designated investigator site staff is required to respond to the query and confirm or correct the data. If the electronic query system is not used, a paper Data Query Form will be faxed to the site. Site personnel will complete and sign the faxed copy and fax it back to Novartis staff that will make the correction to the database. The signed copy of the Data Query Form is kept at the investigator site.

Concomitant medications entered into the database will be coded using the WHO Drug Reference List, which employs the Anatomical Therapeutic Chemical classification system. Concomitant procedures, non-drug therapies and AEs will be coded using the Medical dictionary for regulatory activities (MedDRA) terminology.

Laboratory samples will be processed centrally and the results will be sent electronically to Novartis (or a designated CRO).

ECG readings will be processed centrally and the results will be sent electronically to Novartis (or a designated CRO).

MRI image analysis will be processed centrally and the results will be sent electronically to Novartis (or a designated CRO).

All patient questionnaires will be completed using an electronic device, processed centrally and sent electronically to Novartis (or a designated CRO).

Randomization codes and data about study drug dispensed to the patient and all dosage changes will be tracked using an IRT. The system will be supplied by a vendor, who will also manage the database. The database will be sent electronically to Novartis (or a designated CRO).

Each occurrence of a code break via IRT will be reported to the clinical team and monitor. The code break functionality will remain available until study shut down or upon request of Novartis.

The occurrence of relevant protocol deviations will be determined. After these actions have been completed and the database has been declared to be complete and accurate, it will be locked and the treatment codes will be unblinded and made available for data analysis. Any changes to the database after that time can only be made after written agreement by Novartis Development management.

8.4 Data Monitoring Committee

Not required.

8.5 Adjudication Committee

Not required.

9 Data analysis

The analysis will be conducted on all patient data after data base lock for the respective trial periods. Any data analysis carried out independently by the investigator should be submitted to Novartis before publication or presentation.

9.1 Analysis sets

The following analysis sets will be used in this trial:

Randomized set: The randomized set will be defined as all patients who were randomized. Unless otherwise specified, miss-randomized patients (miss-randomized in IRT) will be excluded from the randomized set.

Full analysis set (FAS): The FAS will be comprised of all patients from the randomized set to whom study treatment has been assigned. Following the intent-to-treat principle, patients will be evaluated according to the treatment assigned to at randomization. For patients randomized erroneously into the wrong stratum, the actual stratum will be used for analyses.

Safety set: The safety set includes all patients who took at least one dose of study treatment during the treatment period. Patients will be evaluated according to treatment received.

9.2 Patient demographics and other baseline characteristics

Summary statistics will be presented for continuous demographic and baseline characteristics for each treatment group and for all patients in the randomized set. The number and percentage of patients in each category will be presented for categorical variables for each treatment group and for all patients.

9.3 Treatments

Study treatment

The analysis of study treatment data will be based on the safety set.

The duration of exposure to study treatment will be summarized by treatment group. In addition, the number of patients with exposure of certain thresholds will be displayed. Compliance will be calculated based on documented study drug administrations and syringe counts and displayed by treatment group.

Prior and concomitant treatment

Prior and concomitant treatments and non-drug therapies will be summarized by treatment group in separate tables.

Prior treatments are defined as treatments taken and stopped prior to first dose of study treatment. Any treatment given at least once between the day of first dose of randomized study treatment and the last day of study visit will be a concomitant treatment, including those which were started pre-baseline and continued into the treatment period.

Treatments will be presented in alphabetical order, by Anatomical Therapeutic Classification codes and grouped by anatomical main group. Tables will also show the overall number and percentage of patients receiving at least one treatment of a particular Anatomical Therapeutic Classification.

9.4 Analysis of the primary variable

9.4.1 Variable

The primary endpoint variable is the percentage of patients with resolution of Achilles tendon enthesitis as assessed by the respective subcomponent of the LEI at 24 weeks. This resolution is referred to as 'response' below.

9.4.2 Statistical model, hypothesis, and method of analysis

The null hypothesis to be rejected is that the odds of response Week 24 are equal in both treatment groups. The corresponding alternative hypothesis is that the odds of response at Week 24 are higher under secukinumab compared to placebo.

Let pj denote the proportion of responders at Week 24 for treatment group j, j=0, 1, where

- 0 corresponds to placebo
- 1 corresponds to secukinumab

The following hypotheses will be tested:

H0: (p1 / (1 - p1)) / (p0 / (1 - p0)) = 1 versus HA: $(p1 / (1 - p1)) / (p0 / (1 - p0)) \neq 1$

In other words:

HA: The odds ratio of achieving a response at Week 24 for secukinumab vs Placebo is different from 1.

The primary analysis will be performed comparing treatments with respect to the primary efficacy variable in a logistic regression model with the factors treatment, $TNF\alpha$ inhibitor status and stratification factor diagnosis (PsA or axSpA). The odds ratio and its 95% confidence interval and p-value will be given.

9.4.3 Handling of missing values/censoring/discontinuations

This study aims to estimate the magnitude of treatment effects that are obtainable under the respective treatments. The disease activity is expected to decrease in the course of treatment. If a patient drops out or discontinues the trial prematurely, the last observed value of that patient seems to be a proper estimate for the effect achieved in that patient.

For the primary endpoint, a patient with a missing assessment will be considered as a responder if he/she has met the response criterion already at the time of drop-out. Otherwise he/she will be considered as a non-responder.

For the confirmatory analyses of secondary endpoints related to physician's/patient's global assessment and SF-36, missing values will be replaced by the last observed value in that patient (Last Observation Carry Forward). In case of a substantial number of missing values, alternative approaches (RMREM, MI) may be additionally calculated as sensitivity analyses.

9.4.4 Sensitivity analyses

A possible effect modification of patient characteristics will be explored by subgroup analyses for sex, age class, $TNF\alpha$ inhibitor status and disease severity at Baseline. The primary model

may also be recalculated with these factors included as well as with respective terms for a subgroup*treatment interaction. In case of a substantial number of missing values, alternative approaches to handle missing values (RMREM, MI) may be additionally calculated as sensitivity analyses.

9.5 Analysis of secondary variables

9.5.1 Efficacy variables

9.5.1.1 Heel pain

The mean change from Baseline of heel pain at 24 weeks, measured on a 10-point NRS will be analyzed using an Analysis of covariance (ANCOVA)-model with factors treatment, country and diagnosis (PsA or axSpA) and with covariate baseline heel pain. The adjusted (LS-) mean difference will be calculated as a point estimate together with its corresponding 95% confidence interval and p-value.

9.5.1.2 Percentage of patients with an improvement of bone marrow oedema

The percentage of patients with an improvement of bone marrow oedema will be analyzed using a logistic regression model analogous to the one described above for the primary endpoint.

9.5.1.3 Physician's/patient's global assessment

Physician's/patient's global assessment, measured on a VAS scale will be analyzed using an ANCOVA model analogous to that used for heel pain.

9.5.1.4 SF-36

The score of the SF-36 will be analyzed using an ANCOVA model analogous to that used for heel pain.

9.5.1.5 Time courses of primary and secondary endpoints

[figure not shown]
The time courses of primary and secondary endpoints (percentage of patients with resolution of Achilles tendon enthesitis, heel pain NRS and Physician's / patient's global assessment, VAS) will be summarized descriptively for all visits from Baseline until Week 52. Summary statistics will include relative and absolute frequencies for the binary variable 'resolution of enthesitis', and the number of patients (N), minimum, mean, median and maximum for the NRS/VAS variables. Additionally, these time courses will be displayed graphically.

9.5.1.6 Preplanned subgroup analyses

The primary endpoint (percentage of patients with resolution of Achilles tendon enthesitis) will additionally be analyzed separately for the subgroups of patients with PsA or axSpA as well as TNF α inhibitor status, using the same model as for the respective pooled, overall population tests. Those subgroup analyses within PsA or axSpA patients are included in the confirmatory testing strategy (see below). Additional subgroup analyses may be conducted post-hoc as required as exploratory evaluations only.

9.5.1.7 Confirmatory testing strategy

The primary endpoint will be confirmatorily tested in the pooled, overall population as well as in the two complementary subgroups of patients with PsA or axSpA.

If the null hypotheses has been rejected for the overall population, it will then be tested for both subgroups simultaneously, both at the significance level 0.05. If the null-hypothesis is false for the overall population, it can logically not be true for both complementary subgroups. Therefore both subgroups can be tested at the same significance level $\alpha = 0.05$ without any further adjustments for multiplicity of subgroups. This procedure provides strong control of the familywise type-I-error at $\alpha = 0.05$.

All secondary endpoints will be tested exploratively outside the confirmatory framework.

9.5.2 Safety variables

9.5.2.1 Adverse events

Treatment emergent adverse events (events started after the first dose of study treatment or events present prior to the first dose of study treatment but increased in severity based on preferred term) will be summarized.

Adverse events will be summarized by presenting, for each treatment group, the number and percentage of patients having any AE, having an AE in each primary system organ class and having each individual AE (preferred term). Summaries will also be presented for AEs by severity and for study treatment related AEs. If a patient reported more than one adverse event with the same preferred term, the adverse event with the greatest severity will be presented. If a patient reported more than one adverse event within the same primary system organ class, the patient will be counted only once with the greatest severity at the system organ class level, where applicable. Serious adverse events will also be summarized.

These summaries may be presented separately by study periods, i.e., Weeks 1-24 and after Week 24.

Separate summaries will be provided for death, serious adverse event, other significant adverse events leading to discontinuation and adverse events leading to dose adjustment (including study treatment discontinuation).

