7.1 Adverse events

An adverse event (AE) is any untoward medical occurrence (e.g., any unfavorable and unintended sign [including abnormal laboratory findings], symptom or disease) in a subject or clinical investigation subject *after providing written informed consent* for participation in the study until the end of study visit. Therefore, an AE may or may not be temporally or causally associated with the use of a medicinal (investigational) product.

In addition, all reports of intentional misuse and abuse of the product are also considered an adverse event irrespective if a clinical event has occurred.

The occurrence of adverse events must be sought by non-directive questioning of the patient at each visit during the study. Adverse events also may be detected when they are volunteered by the patient during or between visits or through physical examination findings, laboratory test findings, or other assessments.

Abnormal laboratory values or test results constitute adverse events only if they fulfill at least one of the following criteria:

- they induce clinical signs or symptoms,
- they are considered clinically significant,
- they require therapy.

Clinically significant abnormal laboratory values or test results must be identified through a review of values outside of normal ranges/clinically notable ranges, significant changes from baseline or the previous visit, or values which are considered to be non-typical in patient with underlying disease. Investigators have the responsibility for managing the safety of individual patient and identifying adverse events. Alert ranges for laboratory and other test abnormalities are included in Appendix 1.

Adverse events must be recorded in the Adverse Events eCRF under the signs, symptoms or diagnosis associated with them, accompanied by the following information:

- the severity grade
 - mild: usually transient in nature and generally not interfering with normal activities
 - moderate: sufficiently discomforting to interfere with normal activities
 - severe: prevents normal activities
- its relationship to the study treatment (Yes/No)
- its duration (start and end dates) or if the event is ongoing an outcome of not recovered/not resolved must be reported.
- whether it constitutes a serious adverse event (SAE See Section 7.2 for definition of SAE) and which seriousness criteria have been met.
- action taken regarding study treatment

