9.5.2.2 Laboratory data

The summary of laboratory evaluations will be presented for three groups of laboratory tests (hematology, serum chemistry and urinalysis). Descriptive summary statistics for the change from Baseline to each study visit will be presented.

These descriptive summaries will be presented by test group, laboratory test and treatment group. Change from Baseline will only be summarized for patients with both Baseline and Post-Baseline assessments.

For each parameter, the maximum change from Baseline within each study period will be analyzed analogously.

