#### 2.1.1 General definitions

**Study treatment:** Study treatment refers to:

Secukinumab 150 mg provided in 1 ml PFS or Secukinumab placebo provided in 1 ml PFS.

**Study treatment start and end date:** Study treatment start date is defined as the first date when a non-zero dose of study drug is administered and recorded on the Drug Administration Record (DAR) CRF page. Similarly, study drug end date is defined as the last date when a non-zero dose of study drug is administered and recorded on the DAR CRF page of the core study.

**Study day:** Study day will be calculated as (event date – study drug start date + 1 day) for events that occurred on or after study drug start date (e.g.visit, lab samples, AEs). For events prior to study drug start date (e.g., time of diagnosis), study day will be negative and calculated as (event date – study drug start date). Note that study drug start date is study day 1 and the day before study drug start date is study day -1 (i.e. no study day 0).

Due to the study drug dosing schedule, one month will be considered as 28 days. However, for “time since event” data (e.g., medical history), one month will be considered as 365.25/12 days for events that occurred prior to study Day 1. Time from events prior to the start of study drug, e.g., time since diagnosis, is calculated as the difference between the start date of study drug and the date of prior event.

Note that, the first dose day is Day 1, and the day before the first dose day is counted as Day -1 (not Day 0).

**Baseline and post baseline:** In general, a *baseline* value refers to the last measurement made prior to administration of the first dose of study treatment. A post-baseline value refers to a measurement taken after the first dose of study treatment.

**Treatment Period:** There are two treatment periods for this study defined as :

Treatment Period 1 is defined as a 24 Week placebo-controlled, double-blind treatment period starting from baseline till Week 24.

Treatment Period 2 is a 28 Week open-label treatment period starting from Week 28 (end of Week 24) till Week 52.

**Lost to follow up:** The patients whose study completion status is unclear because they fail to appear for study visits without stating an intention to withdraw.

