**Table 2.8-2 CTCAE grades for laboratory parameters to be analyzed**

CTCAE Term	Grade 1	Grade 2	Grade 3	Grade 4
HGB decreased (Anemia)	<LLN - 100 g/L	<100 - 80 g/L	<80 g/L	
Platelet count decreased	<LLN - 75.0 x10e9 /L	<75.0 - 50.0 x10e9 /L	<50.0 - 25.0 x10e9 /L	<25.0 x 10e9 /L
White blood cell decreased	<LLN - 3.0 x 10e9 /L	<3.0 - 2.0 x 10e9 /L	<2.0 - 1.0 x 10e9 /L	<1.0 x 10e9 /L
Neutrophil count decreased	<LLN - 1.5 x 10e9 /L	<1.5 - 1.0 x 10e9 /L	<1.0 - 0.5 x 10e9 /L	<0.5 x 10e9 /L
Lymphocyte count decreased	<LLN - 0.8 x 10e9/L	<0.8 - 0.5 x 10e9 /L	<0.5 - 0.2 x 10e9 /L	<0.2 x 10e9 /L
Creatinine increased*	>1 - 1.5 x baseline; baseline; >ULN - 1.5 x ULN	>1.5 - 3.0 xULN	>3.0 baseline; >3.0 - 6.0 x ULN	>6.0 x ULN
TBL increased	>ULN - 1.5 x ULN	>1.5 - 3.0 x ULN	>3.0 - 10.0 x ULN	>10.0 x ULN
GGT increased	>ULN - 2.5 x ULN	>2.5 - 5.0 x ULN	>5.0 - 20.0 x ULN	>20.0 x ULN
ALT increased	>ULN - 3.0 x ULN	>3.0 - 5.0 x ULN	>5.0 - 20.0 x ULN	>20.0 x ULN
AST increased	>ULN - 3.0 x ULN	>3.0 - 5.0 x ULN	>5.0 - 20.0 x ULN	>20.0 x ULN
ALP increased	>ULN - 2.5 x ULN	>2.5 - 5.0 x ULN	>5.0 - 20.0 x ULN	>20.0 x ULN

Glucose increased (Hyperglycemia)	>ULN - 8.9 mmol/L	>8.9 - 13.9 mmol/L	>13.9 - 27.8 mmol/L	>27.8 mmol/L
Glucose decreased (Hypoglycemia)	<LLN - 3.0 mmol/L	<3.0 - 2.2 mmol/L	<2.2 - 1.7 mmol/L	<1.7 mmol/L
Cholesterol high Hypertriglyceridem ia	mmol/L 1.71 - 3.42 mmol/L	>7.75 - 10.34 mmol/L >3.42 - 5.7mmol/L	mmol/L >5.7 - 11.4 mmol/L	>12.92 mmol/L >11.4 mmol/L

\*Note: for "creatinine increased" the baseline criteria do not apply

Shift tables will be presented comparing baseline laboratory result (CTCAE grade) with the worst results (expressed in CTCAE grade) during the treatment phase (either initial or entire) analyzed. Of note, baseline will be defined as last assessment prior to first dosing in initial treatment phase. Patients with abnormal laboratory values will be listed and values outside the normal ranges will be flagged.

Summaries for newly occurring or worsening clinically notable lipid abnormalities will also be provided cumulatively for each of the following parameters and categories:

- HDL:
  - $\leq LLN$
  - $<0.8 \times LLN$
- LDL, cholesterol, triglycerides:
  - $\geq ULN$
  - $>1.5 \times ULN$
  - $>2.5 \times ULN$

Newly occurring or worsening liver enzyme abnormalities will also be summarized based on the event criteria given in Table 2.8-3:

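### Safety baseline and treatment-emergence are not reset when placebo patients switch to secukinumab at Week 24, so placebo-period change can enter their longer-term safety results

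*Protocol*

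**What the plan says.** Protocol 9.5.2.1 defines treatment-emergent adverse events as those with onset after the first study dose and "events present prior to the first dose of study treatment but increased in severity based on preferred term"; SAP 2.8.1 uses the same definition. SAP 2.1.1 defines study treatment as "Secukinumab 150 mg provided in 1 ml PFS or Secukinumab placebo provided in 1 ml PFS", so in Group 2 the reference dose is the first placebo injection.

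The general baseline in SAP 2.1.1 is the last measurement before that same dose. For the laboratory grade shifts, SAP 2.8.3 (note to Table 2.8-2) is explicit: "baseline will be defined as last assessment prior to first dosing in initial treatment phase".

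All Group 2 patients move to secukinumab at Week 24 (Protocol 3.1 and 5.2). On reporting periods, the protocol says "These summaries may be presented separately by study periods, i.e., Weeks 1-24 and after Week 24". SAP 2.8 plans two: Weeks 1-24 and the entire treatment period. For laboratory data both documents add that, for each parameter, "the maximum change from Baseline within each study period will be analyzed analogously". SAP 2.8.3, 2.8.4.1 and 2.8.4.2 also plan shifts to the most extreme value and summaries or listings of newly occurring abnormalities. No section defines a second baseline or a second reference severity at the switch.

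**The concern.** The safety objective concerns secukinumab, and for Group 2 secukinumab starts about 24 weeks after the reference point. Two consequences follow.

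For laboratory values and vital signs, a change during placebo treatment is carried into every later comparison. A post-switch value may look changed when nothing has happened since secukinumab began. A real change on secukinumab may be hidden if it reverses an earlier drift on placebo.

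For adverse events, the worsening limb looks only at events already present before the first study dose. An event that began on placebo and became more severe on secukinumab is treatment-emergent because of its placebo onset; the later worsening has no standing of its own. The plan also presents the greatest severity per preferred term. Depending on how the event is recorded, a grade reached on secukinumab could be shown against an event that began on placebo.

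**Working it through.** The plan states no figure for this point, so there is nothing to reproduce. The check applies the written rules to a Group 2 patient who switches on Day 169 (Week 24 in Protocol Table 6-1), and then sizes the exposure concerned.

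**Adverse events.** Days 60 and 200 are illustrative days on placebo and on secukinumab.

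| History | Treatment-emergent as written? | Through what |
|---|---|---|
| A. New onset Day 200 | Yes | Onset, on secukinumab |
| B. Mild before Day 1, worse Day 200 | Yes | Worsening limb, which has no end date |
| C. Mild onset Day 60, worse Day 200 | Yes | Onset on placebo only; the worsening adds nothing |
| D. Mild before Day 1, worse Day 60, worse again Day 200 | Yes | Worsening on placebo only; the second worsening adds nothing |

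No event is lost from the treatment-emergent tables. The gap is confined to C and D.

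**Laboratory and vital signs.** In Table 6-1 the scheduled post-baseline laboratory visits are Weeks 2, 4, 8, 12, 16, 20, 24, 36 and 52. Protocol 6.5 puts blood draws and safety assessments before dosing, so the Week 24 value still belongs to placebo. For Group 2, 7 of the 9 scheduled values therefore precede secukinumab and 2 follow it. For vital signs entered in the clinical database (Weeks 8, 16, 24, 36, 52), the split is 3 and 2.

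Take a Group 2 patient with ALT normal at baseline, above 3×ULN at Week 16, and normal at Weeks 24, 36 and 52. The entire-period worst grade and the newly occurring ALT criterion in Table 2.8-3 are both met, entirely from placebo. If instead ALT had stayed at the raised level through Weeks 24 and 36, the Week 36 change from baseline and the maximum change after Week 24 would show a rise, although nothing changed after the first secukinumab dose.

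**Exposure governed by the rule.** Inputs: 100 per arm (Protocol 9.8); 24 weeks, then 28 weeks (SAP 2.1.1); drop-out *d* before Week 24 assumed to be 0 to 20%. The middle value, 11%, is 100 − 89 from Protocol 9.8, where the allowance covers drop-outs and other protocol violations together.

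- Group 1 secukinumab weeks = 100×24 + 100(1−*d*)×28
- Group 2 secukinumab weeks = 100(1−*d*)×28

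| *d* | Group 1 | Group 2 | Group 2 share | Group 2 patient-years (weeks×7/365.25) |
|---|---|---|---|---|
| 0 | 2,400 + 2,800 = 5,200 | 2,800 | 2,800/8,000 = 35.0% | 53.7 |
| 0.11 | 2,400 + 2,492 = 4,892 | 2,492 | 2,492/7,384 = 33.7% | 47.8 |
| 0.20 | 2,400 + 2,240 = 4,640 | 2,240 | 2,240/6,880 = 32.6% | 42.9 |

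The formula credits Group 1 drop-outs with the full 24 weeks. If they left at once, the share would be 28/(52+28) = 35.0% whatever *d* is, so 33-35% covers both extremes.

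**The case against.** The strongest reply on adverse events is that the gap may not arise in practice. Protocol 7.1 lists a severity grade and start and end dates, and requires changes in severity to be assessed at each visit, but does not say how a change is entered. If worsening opens a new record, its start date falls after the switch and it is an ordinary emergent event. If one record keeps only its worst grade, the date of worsening is not among the listed items, and no re-anchored rule could be programmed. This stands: the adverse-event half depends on an eCRF convention that the documents do not give.

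On laboratory data, the fixed baseline is a stated choice, the summaries are descriptive, and by-visit tables put Week 24 beside Weeks 36 and 52, so average drift on placebo is visible. Abnormal values are also listed. That answers much of the worry about mean changes. It does not answer the worst-value shifts and newly occurring flags, which cover the initial or the entire phase and have no post-switch version.

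It can also be said that the point cannot be separated from where switched patients' results are displayed, which the SAP leaves open. That is fair, and any fix must therefore bring its own post-switch summary.

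Three stronger readings are tempting but unsupported:

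- **Worsening on secukinumab is never counted for any switched patient.** Histories A and B show that new onsets, and pre-Day 1 events that first worsen after the switch, meet the definition.
- **A third of secukinumab events are misclassified.** The 33-35% is person-time. The affected events are those ongoing at the switch that later worsen, and the documents give no basis for counting them.
- **The SAP already re-anchors Group 2**, because it says "Study treatment start date is defined as the first date when a non-zero dose of study drug is administered" and the protocol glossary reserves study drug for the product under test. The same SAP section includes placebo in study treatment and starts Treatment Period 1 at baseline, and the laboratory note names the initial phase.

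**Conclusion.** The point holds in a limited form. For Group 2 after Week 24, the plan compares laboratory values and vital signs with a reference taken before about 24 weeks of placebo, and its entire-period worst-value and newly occurring summaries can report placebo-period changes. This part follows directly from the stated baseline rules. For adverse events, the plan lacks a rule for events that began or already worsened on placebo and then worsen on secukinumab; whether that matters depends on how worsening is recorded.

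The rule governs about 33-35% of planned secukinumab time (43 to 54 patient-years), given 100 per arm and 0-20% drop-out. The number of results affected cannot be derived from the documents. The placebo-controlled comparison to Week 24 and the efficacy analyses are untouched. The change is worth making because the reference values it needs are already scheduled.

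**What to change.** Keep the current anchor for Day 1 to Week 24. In SAP 2.8.1, 2.8.3 and 2.8.4.2, add a post-switch summary for Group 2:

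- **Laboratory and vital signs.** Take the last value before the first secukinumab dose (the pre-dose Week 24 value) as baseline for changes, shifts and newly occurring abnormalities, and count only post-switch values.
- **Adverse events.** Count an event as emergent on secukinumab if it starts on or after the date of the first secukinumab dose, or was ongoing at that dose and then increased in severity.
- **Recording.** Confirm that the eCRF dates worsening, either as a new record or as a dated grade. Without this, the second limb cannot be derived.
- **Partial dates.** SAP 5.1.2 compares partial adverse-event dates only with treatment start. A date known only to the switch month becomes the first of that month, which can fall before the switch. For this flag, compare with the first secukinumab dose date as well.

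ECG is left out, because Table 6-1 schedules none at Week 24. The cost is one derived baseline, one flag and one set of tables. The laboratory and vital-sign part needs no new data; the adverse-event part needs none if worsening is already dated. With only Weeks 36 and 52 scheduled for laboratory tests after the switch, the new tables will be sparse.
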